7.2 Primary objective

The primary objective is to evaluate safety, acceptability and implementation feasibility of the Salutare One Referral Software.

7.3 Secondary objectives

Determination of the following metrics with and without the use of the Salutare One Referral software:

Title: Salutare Dialogue for MDTs					
Authors	[name], [name], [name]	Ver.2		Date Authorised	22/01/2025

- (1) MDT administration time
- (2) Completeness of pre-assessment information
- (3) Clinical engagement
- (4) Time spent by MDT panel members attending meetings
- (5) MDT performance rating
- (6) Duration of MDT per-patient discussion time
- (7) Overall time for MDT meetings
- (8) Time from referral submission to the generation of MDT definitive decisions.
- (9) Time from referral submission to the implementation of MDT recommendations (OPTIONAL)
- (10) Number and rate of cases re-presented for MDT review – breast cancer only
- (11) Drug changes to accommodate surgery or any disease optimisation advice
- (12) Presence or absence of peri-operative and post-operative complications (OPTIONAL)

8. Study Design

The study is designed as a mixed-methods prospective Before and After Study.

8.1 Primary Endpoint

The determination of the Salutare One Referral Software safety, implementation feasibility and user acceptability in facilitating effective MDT meetings. One Referral software System Usability Score (SUS) and user questionnaires will be administered to MDT panel members. The intent is to utilise the current study's primary endpoint to inform a future protocol amendment and study expansion to further sites to test for clinically relevant and patient relevant outcomes.

8.2 Secondary endpoints

Determination of the following metrics with and without the use of the Salutare One Referral software:

Measure	Assessed via
(1) MDT administration time	Participant questionnaire MDT meetings observation dataset
(2) Completeness of pre-assessment information 
 • Medical history • Risk score completion • TNM recording (radiological and pathological) – breast cancer only 	Participant questionnaire MDT meetings observation dataset Note: If access to the patient's medical record is required, for example if any aspects of the pre-assessment information are missing in the forms, the data would be provided by a member of the direct care team.
(3) Clinical engagement	Participant questionnaire MDT meetings observation dataset
(4) Time spent by MDT panel members attending meetings	Participant questionnaire MDT meetings observation dataset
(5) MDT performance rating	Participant questionnaire

Title: Salutare Dialogue for MDTs					
Authors	[name], [name], [name]	Ver.2		Date Authorised	22/01/2025

(6) Duration of MDT per-patient discussion time	Participant questionnaire MDT meetings observation dataset
(7) Overall time for MDT meetings	Participant questionnaire MDT meetings observation dataset
(8) Time from referral to the generation of MDT recommendation	MDT meetings observation dataset Note: If access to the patient's medical record is required, for example if the MDT recommendation date is not clear in the forms, the data would be provided by a member of the direct care team.
(9) Time from referral to the implementation of MDT recommendations (OPTIONAL) 
 • “Decision to Treat” (cancer MDT) • Date of operation (Anaesthetics) 	MDT meetings observation dataset Participant questionnaire Note: If access to the patient's medical record is required, for example if any aspects of the pre-assessment information are missing in the forms, the data would be provided by a member of the direct care team.
(10) Number and rate of cases represented for MDT review – breast cancer only	MDT meetings observation dataset MDT meetings recordings MDT referral form (local form or Salutare One Referral form – PDF extract)
(11) Drug changes to accommodate surgery or any disease optimisation advice.	MDT meetings observation dataset
(12) Presence or absence of peri-operative and immediate post-operative complications	Medical records to be reviewed by a member of the NHS direct care team

8.3 The Study Evaluation Model

A Logic Model is used as a theory-based approach to explicitly articulate the underlying theory of change which shapes the desired outcomes and impacts achieved by the Salutare One Referral software as per the study hypothesis (Kaplan and Garrett, 2005; Hayes et al., 2011; Helitzer et al., 2010; Friedman & Wyatt 2006).

Title: Salutare Dialogue for MDTs					
Authors	[name], [name], [name]	Ver.2		Date Authorised	22/01/2025

How Salutare Dialogue can lead to better patient outcomes & NHS resource use

Key: Sources are in bold italic, eg *"Raine 2014"*

[figure not shown]

Figure 1: One Referral Logic Model

The chosen secondary endpoints are the observed clinical outputs. The study is a pilot project and therefore not powered to collect data on health outcomes mediated by the clinical outputs. Note: The patient communication module is currently not yet available and therefore will not be assessed in the present study. Observing the duration of MDT per-patient discussion time with and without One Referral contributes to understanding the software's influence on MDT efficiency. This endpoint sheds light on whether One Referral facilitates more concise and productive discussions among team members.

User questionnaires assessing MDT discussions' effectiveness and referral information completeness with and without One Referral provide further qualitative data on the software's impact. Lastly, evaluating MDT preparation time through user questionnaires offers insights into the software's efficiency in streamlining preparatory tasks.

The System Usability Score (SUS) (Brooke, 1996), the only validated tool used in this study, offers valuable insights into the acceptability of the One Referral software. SUS is a simple, widely used 10-statement survey that asks users to rate their level of agreement or disagreement to the 10 statements (half worded positively, half worded negatively) about the software under review.

Usability research within the human-computer interaction field shows that user scores differ substantially over time, with users reporting more favourable scores as they expand their experience with the product (Mendoza and Novick, 2005; McLellan, 2012). Repeated observations of a group of users over time are recommended in order to follow up changes with respect to one or more evaluation variables., with initial use evaluation affording insights on 'discoverability' or 'learnability' and further evaluations elucidating true usability experiences.

8.4 Risk Scores

Breast Risk Scores

Title: Salutare Dialogue for MDTs					
Authors	[name], [name], [name]	Ver.2		Date Authorised	22/01/2025

PREDICT (Wishart GC et al, 2010) is a risk score that shows how different treatments for early invasive breast cancer might improve survival rates after surgery. It is widely used in breast cancer MDTs and by the Royal Free Breast Cancer team. It is an important clinical decision-making factor for the MDT outcomes and its completion rate in referrals before and after the implementation of One Referral software will be assessed.

Anaesthetic risk scores

The ASA (American Society of Anesthesiologists) Physical Status Classification System (ASA. 2024) is a tool used to assess peri-operative risks for surgical patients. This system categorises patients into six classes based on their preoperative health status, ranging from ASA I (healthy) to ASA VI (brain-dead organ donor).

The SORT is a tool designed to predict the risk of death within 30 days after inpatient surgery. Developed through a collaboration between NCEPOD researchers (Protopapa and Smith, 2014) and clinicians at the UCL/UCLH Surgical Outcomes Research Centre, the SORT model has undergone various evaluations in different patient groups and contexts since its initial release. It is recommended to use this model, incorporating clinical estimates from senior decision-makers and, ideally, the input of a multidisciplinary team.

In this study, the ASA Physical Status Classification System and SORT scores will be employed to evaluate patients' peri-operative risk profiles. The presence or absence of the scores in the pre-assessment documentation will be evaluated as one of the key indicators of the pre-assessment information completeness.

8.5 Statistical Analysis

This study will employ a descriptive approach to analyse the collected data. Prior to finalising the statistical approach, the distribution of key variables will be assessed. In cases where variables show significant skewness, data transformation techniques, such as logarithmic transformation, will be considered to improve normality.

Patient records discussed by the MDT panels will be reviewed and analysed. For the complex case MDTs (RNOH Anaesthetics MDT and Royal Free Colorectal Cancer MDT), all cases discussed during the study pre-intervention, intervention and post-intervention phases will be included in the study analysis.

For the high-volume MDTs (Royal Free Breast Cancer MD), approximately 25% cases are expected to be submitted using Salutare One Referral during the intervention period. A formal comparison of the pre-intervention and intervention study cohort will be made. At the end of the study, raw data will be processed for summary and descriptive statistics. The distribution of times from referral to MDT decision & implementation will be assessed to check if mean or median most appropriate to use.

Normally distributed data will be reported as means with 95% confidence intervals (CIs), while non-normally distributed data will be presented as medians with interquartile ranges (IQRs). Categorical variables will be summarized using proportions or percentages, accompanied by their corresponding 95% CIs.

Pending normality testing using the Kolmogorov-Smirnov Test, a combination of Multivariate Mixed-Effects Models and Generalized Linear Mixed Models (GLMMs), the latter for categorical, ordinal, and binary measures, will be carried out for comparing the system usability scales the acceptance of the null hypothesis.

Title: Salutare Dialogue for MDTs					
Authors	[name], [name], [name]	Ver.2		Date Authorised	22/01/2025

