Target	
RNOH Anaesthetic MDT: Approximately 20 staff taking part in MDT meeting taking part in the MDT meeting preparation and discussion. We aim to collect data for approximately 40 cases discussed without the Salutare One Referral software and approximately 40 patients discussed with Salutare One Referral.
 
Royal Free (Colorectal Cancer): Approximately 20 staff taking part in MDT meeting taking part in the MDT meeting preparation and discussion. We aim to collect data for approximately 120 cases discussed without the Salutare One Referral software and approximately 120 cases discussed with Salutare One Referral.
 
Royal Free (Breast Cancer): Approximately 50 staff taking part in the MDT meeting preparation and discussion. We aim to collect data for approximately 150 cases discussed without the Salutare One Referral software and 150 patients discussed with Salutare One Referral. (Note: The Royal Free Breast Cancer MDT testing is currently on hold, subject further discussions).
	
Inclusion criteria (Active Study Group)	MDT meeting Panel Members, Coordinators and staff submitting MDT referrals will take part in this study.	
Exclusion criteria (Main study)	MDT meeting Panel Members, Coordinators and staff submitting MDT referrals who are unwilling or unable to take part in the study.	
Duration of study	
The study consists of 4 phases:
 
 1. Pre-intervention period (before-study control) with no access to the Salutare One Referral software. 2. Onboarding period to allow for software installation and staff training and adjustment to the technology 3. Salutare One Referral intervention period 4. Post-intervention period (after-study control) with no access to the Salutare One Referral software 
The total duration of the study will depend on the frequency of MDT meetings and the number of cases discussed.
	

	
 • Stanmore Anaesthetics MDT and Royal Free Colorectal Cancer MDT: The study duration will be approximately 18 weeks (4-week pre-intervention period, 2-week onboarding period, 8-week intervention period, 4-week post-intervention period) • Royal Free Breast Cancer MDT: The study duration will be approximately 10 weeks (2-week pre-intervention period, 2-week onboarding period, 4-week intervention period, and a 2-week post-intervention period). 
Additionally, 4 weeks are allowed to complete the study data collection.

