The Royal Free Breast Cancer MDT meets once per week discussing approximately 90 breast cancer cases, of which there are 60 new cases and 30 roll over cases (cases brought back due to insufficient information). The team comprises MDT Coordinators, Breast Surgeons, Oncologists, Radiologists, Pathologists and Senior Nurse Specialists. The MDT focuses on discussing all breast cancer cases in the breast cancer treatment pathway. Each case undergoes team discussion of cases referred following triple assessment or other pathways. The MDT involvement in this study will be led by the Breast Service Clinical Lead, [name], Consultant Breast Surgical Oncologist and Reconstructive Surgeon.

At present, the MDT operates without specialised software. Typically, Consultants submit referrals to the MDT Coordinator who lists the cases, and the history is presented verbally with minimal information (name, site of lesion, and essential facts) listed in a single short paragraph. The list typically contains the information for 10 patients on a single side of A4 and is printed and discussed freehand. Approximately 30% of new cases need re-presentation due to missing critical information, resulting in delays in patient pre-operative pathways.

7. Objectives

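### Breast MDT: 25% software use over four weeks gives about 90 software cases, not the target of 150, and the protocol does not say which cases form the intervention cohort

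*Protocol*

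**What the plan says.** Section 1 (Target) plans, for the Royal Free Breast Cancer MDT, "approximately 150 cases discussed without the Salutare One Referral software and 150 patients discussed with Salutare One Referral". The same section and section 14 give the phases as "2-week pre-intervention period, 2-week onboarding period, 4-week intervention period, and a 2-week post-intervention period". Section 6 describes a team that "meets once per week discussing approximately 90 breast cancer cases", made up of "60 new cases and 30 roll over cases".

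Section 8.5 then treats the MDTs differently. For the two complex-case MDTs, "all cases discussed during the study pre-intervention, intervention and post-intervention phases will be included in the study analysis". For the breast MDT there is no such sentence. The text says that "approximately 25% cases are expected to be submitted using Salutare One Referral during the intervention period", and follows with "A formal comparison of the pre-intervention and intervention study cohort will be made". It does not say which breast cases make up the intervention side of that comparison, or by what rule a case comes to be submitted through the software.

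Sections 1 and 6 note that testing in this MDT is on hold.

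**The concern.** There are two linked problems.

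The first is arithmetic. The target, the expected uptake, the weekly caseload and the phase length are all in the protocol, and they do not fit together.

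The second is what the comparison would mean. If the intervention cohort is the software quarter, it is a subset formed by an unstated process and set against an unselected pre-phase series. A difference could then reflect who referred or what kind of case was entered. If the cohort is every case in the intervention period, about three quarters of it never passed through the software, and a real effect is averaged down. Overall meeting time cannot be split by case, so it is diluted under either definition.

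This is the only high-volume setting in the study and the only MDT in which re-presentation (secondary endpoint 10) is assessed. Section 1 says the endpoints will inform later amendments and expansion, so a spurious gain or a hidden benefit here would carry forward.

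**Working it through.** **Inputs.** About 90 cases a week at one weekly meeting, of which 60 are new and 30 roll-over (section 6); a 4-week intervention (sections 1 and 14); about 25% software use (section 8.5); a target of 150 with and 150 without the software (section 1).

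**Attempt to reproduce the 150 with software.** Software cases = cases per week x weeks x share.

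- All cases, 4 weeks: 90 x 4 x 0.25 = 90, which is 60% of 150.
- New cases only, 4 weeks: 60 x 4 x 0.25 = 60, which is 40% of 150.
- All cases, counting the 2 onboarding weeks as well: 90 x 6 x 0.25 = 135.
- New cases over all 10 study weeks: 60 x 10 x 0.25 = 150. This matches only by counting 6 weeks outside the intervention period, so it does not explain the figure.

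**What 150 would require.**

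- Uptake over 4 weeks: 150 / 360 = 41.7% of all cases, or 150 / 240 = 62.5% of new cases.
- Duration at 25%: 150 / 22.5 = 6.7 weeks for all cases, or 150 / 15 = 10 weeks for new cases only.

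**The 150 without software.** The pre-phase alone gives 2 x 90 = 180 (120 if new cases only). Adding the 2-week post-phase gives 360 (240). This side is attainable.

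**Effect on precision.** For a proportion near 30%, the 95% half-width is 1.96 x sqrt(0.3 x 0.7 / n): 7.3 points at n = 150, 9.5 at n = 90 and 11.6 at n = 60.

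**Dilution, if all cases form the cohort.** With a share of 0.25 and no effect on the other cases, all-case difference = 0.25 x difference among software cases. Illustration with assumed rates: section 6 gives about 30% re-presentation among new cases. Take 30% as the baseline for every case, and suppose the software lowers it to 15%. The all-case rate is 0.75 x 30% + 0.25 x 15% = 26.25%, so a 15-point fall shows as 3.75 points.

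**Selection, if software cases form the cohort.** Illustration with assumed rates and no software effect: software users' cases naturally run at 20% and the others at 33.3%, so the overall rate is 0.25 x 20% + 0.75 x 33.3% = 30%. Software cases against the whole pre-phase then show 20% against 30%, a 10-point gain with no effect behind it. This shows that bias is possible. It does not estimate its size.

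**The case against.** Several stronger statements are tempting, and the protocol does not support them.

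- *The 150 cannot be reached.* Durations are approximate, section 10 calls them indicative, and sections 1 and 14 make total length depend on meeting frequency and case numbers. About 6.7 weeks at 25% would do it. The explicit extension example in section 10 concerns cancelled or rescheduled meetings, not a shortfall in cases, but it does not rule out a longer phase. What stands is that the stated values disagree.
- *Referrers choose the quarter.* Section 10.3 has participating clinicians start referrals in the software. Section 15 mentions the existing route as one possible measure where a participant's issues cannot be resolved. Referrer choice is an inference from these; the quarter could equally come from a named list, one clinic or the consented users. What stands is that no rule is given.
- *Every breast result shrinks fourfold.* The factor applies to case-level means and proportions with no spillover to other cases. Section 8.5 plans medians for non-normal data, and a median need not scale by 0.25.

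The dilution reading is also the less supported one for case-level endpoints: the target in section 1 and the objectives in section 7.3 contrast cases with and without the software. Against that, section 12 reports re-presentation as an aggregate over the intervention period or by phase, so the text does not settle the matter.

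Exact analysis sets are often left to a SAP, and that is fair. But the target, uptake and phase length are fixed in the protocol, and how cases enter the software is study conduct. If it is not recorded at the time, no later plan can recover it.

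Finally, the study is described as a descriptive pilot, not powered for secondary outcomes, and no power claim rests on 150. That limits the consequence. It does not remove selection bias from a comparison that section 8.5 itself calls formal.

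**Conclusion.** The concern holds in a limited form. At the stated uptake and duration, the breast MDT yields about 90 software cases (60 if only new cases are entered), a shortfall of 40% to 60% against 150, which is more than the word approximately can cover. The intervention cohort is undefined. One definition is open to selection by referrer or case type. The other dilutes case-level means and proportions to about one quarter, assuming 25% uptake and no effect on non-software cases. Whole-meeting times are diluted under both.

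The severity is minor. Only secondary endpoints are affected, the primary assessment of safety, feasibility and acceptability is untouched, and this MDT is on hold, so nothing collected would be lost by a change.

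**What to change.** 1. Restate the breast software target as about 90 (60 if only new cases are entered), or change the uptake or phase length so that the figures agree.
2. Define the breast intervention cohort as the software cases for case-level endpoints.
3. Log the referrer for every case in every phase, and compare software cases with pre-phase cases from the same referrers.
4. Report all breast cases by phase alongside. Same-referrer comparison does not remove selection of cases within a referrer, and the all-case figures help to show it.
5. Use per-case discussion time, not overall meeting time, to judge the software effect in this MDT.

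Allocating every fourth referral to the software may look cleaner but does not fit the design. The referral is created inside the software by a consenting user, so its route is fixed before it is received. A set share would also override natural uptake, which bears on the feasibility objective.

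The cost is protocol wording, a referrer log, a smaller stated number and fewer comparator cases. For example, if the software users bring a quarter of the pre-phase caseload, same-referrer comparators number about 180 x 0.25 = 45 rather than 180.

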11.4 Post-Study Assessment

Post-study assessment will be administered at the end of the post-study control period. The assessment will comprise the assessment of any safety, efficiency and effectiveness gains/losses associated with discontinuing the use of the Salutare One Referral Software.

12. Data collection from One Referral

KPI type	KPI collected
Engagement with One Referral	Number of users set up on One Referral
	Number of comments by users
	Number of referrals processed by MDTs

This study will employ a mixed reporting strategy to accurately represent different types of data collected throughout the study phases:

Time-Series Reporting:

Variables that can be meaningfully measured and reported for each MDT instance will be presented as a time series. This approach allows for the observation of trends over time and the potential identification of immediate and gradual effects of the Salutare One Referral software implementation. Examples include:

- Number of users engaging with the system per MDT
- MDT preparation time
- Duration of MDT per-patient discussion time
- Overall time for MDT meetings

Aggregate Reporting:

Some metrics are more appropriately reported as aggregate figures over the entire intervention period or for each study phase. Examples include:

- Percentage of cases re-presented to the MDT
- Mean or median time from referral submission to MDT decision implementation

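### If optional endpoint 9 is collected, a plain mean or median time to implementation by phase is distorted by unequal follow-up; an equal window per case would avoid this

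*Protocol*

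**What the plan says.** Endpoint 9 is the time from referral submission to implementation of the MDT recommendation, marked optional. Section 8.2 ends it at the decision to treat for the cancer MDTs and at the date of operation for anaesthetics.

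Section 7.3 sets the purpose: "Determination of the following metrics with and without the use of the Salutare One Referral software". Section 8.5 says of times to decision and implementation that their distribution "will be assessed to check if mean or median most appropriate to use", with means and 95% CIs for normal data and medians with IQRs otherwise. For the complex-case MDTs, "all cases discussed during the study pre-intervention, intervention and post-intervention phases will be included in the study analysis". The sentence "A formal comparison of the pre-intervention and intervention study cohort will be made" stands in the paragraph on the breast MDT, which is on hold.

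Section 12 states: "Some metrics are more appropriately reported as aggregate figures over the entire intervention period or for each study phase". One of its examples is "Mean or median time from referral submission to MDT decision implementation".

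Sections 1, 13 and 14 give the calendar. The complex-case MDTs have 4 weeks pre-intervention, 2 onboarding, 8 intervention and 4 post-intervention. Breast has 2, 2, 4 and 2. A further 4 weeks are allowed to complete data collection. Section 1 labels both the pre- and the post-intervention phase as controls without the software.

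**The concern.** A simple mean needs an implementation date for every case. A case discussed late has less calendar time in which to acquire one. If cases still open at the close drop out, the slow cases are lost, and more are lost in the later phases. Phases can then differ when the software does nothing.

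The measure matters to the sponsor. Section 16.1 says the study will evaluate the pathway from referral to implementation, Section 8.6 expects a shorter pathway, and the synopsis names this measure as an example endpoint for expansion. Section 12 also uses the post-intervention phase to judge whether the software's impact persists, and that phase is followed least.

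**Working it through.** **1. Calendar, from Sections 13 and 14.** Complex-case MDTs: 4 + 2 + 8 + 4 = 18 weeks = 126 days, which reproduces the stated duration and the schedule. Adding 4 weeks gives Day 154 (week 22). Breast: 2 + 2 + 4 + 2 = 10 weeks = 70 days; adding 4 weeks gives Day 98 (week 14).

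**2. Follow-up after discussion = close minus week of discussion.** Taking these dates as the data close for endpoint 9 is an assumption.

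| MDT | Pre | Intervention | Post |
|---|---|---|---|
| Complex-case (weeks 0-4, 6-14, 14-18) | 18-22 wk | 8-16 wk | 4-8 wk |
| Breast (weeks 0-2, 4-8, 8-10) | 12-14 wk | 6-10 wk | 4-6 wk |

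The complex-case phase midpoints are weeks 2, 10 and 16. Under any single close, intervention cases therefore have on average 10 - 2 = 8 weeks less follow-up than pre-intervention cases, and post-intervention cases 16 - 2 = 14 weeks less.

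**3. Assumptions for size.** The protocol gives no time to implementation, so a range is used. There is no software effect. Time from discussion to implementation is exponential with mean m = 2, 4, 8 or 12 weeks. Discussion is uniform within each phase, and the close is week 22. Referral wait is nil, or exponential with mean 2 weeks.

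**4. Share still open at the close.** For a phase running from week a to week b with close C:

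open = m/(b - a) x [exp(-(C - b)/m) - exp(-(C - a)/m)].

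Example, intervention, m = 8: (8/8) x [exp(-8/8) - exp(-16/8)] = 0.3679 - 0.1353 = 23.3%.

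**5. Open cases dropped, no wait** (simulation, 2,000,000 cases per phase):

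| m (wk) | Open, pre/int/post (%) | Median, pre/int/post (wk) | Int vs pre, median | Int vs pre, mean | Post vs pre, median |
|---|---|---|---|---|---|
| 2 | 0.0/0.4/5.9 | 1.39/1.38/1.27 | -1% | -2% | -8% |
| 4 | 0.7/5.9/23.3 | 2.74/2.55/1.94 | -7% | -14% | -29% |
| 8 | 8.3/23.3/47.7 | 4.91/3.87/2.42 | -21% | -27% | -51% |
| 12 | 19.0/37.5/60.9 | 6.24/4.49/2.61 | -28% | -31% | -58% |

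With the 2-week wait, intervention vs pre is 0, -5, -16 and -22% for medians and -1, -9, -20 and -24% for means. For breast with no wait, medians shift by -3, -14, -26 and -31%.

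The exponential shape is not what drives this. With log-normal times (sigma 0.8) and a true median of 60 days, the intervention mean is 14.0 days and the median 10.1 days below pre-intervention.

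**6. Pre and post pooled equally as the control, open cases dropped.** Intervention vs pooled, m = 2, 4, 8, 12:

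- Medians: +4, +10, +8, +5% (no wait); +3, +6, +5, +2% (2-week wait).
- Means: +6, +5, -8, -14% (no wait); +3, +3, -5, -10% (2-week wait).

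**7. Open cases ranked as longest.** Pre vs intervention medians differ by 0 to +1% in all eight settings. Upper quartiles agree at m = 2 and 4. At m = 8 they are 11.09 vs 12.45 weeks (+12%; +16% with the wait), and at m = 12 the quartile is not reached in intervention. Against the pooled control with no wait, the median is -4% at m = 8 and -26% at m = 12. A mean cannot be formed.

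**8. Equal window under the same null.** Assume 20% of recommendations are never implemented. The proportion implemented within 28 days of discussion, all cases in the denominator, is then 50.5/50.5/50.5% (m = 4), 31.4/31.5/31.5% (m = 8) and 22.7/22.7/22.6% (m = 12) for pre/intervention/post. Removing the cases known never to be implemented would bring a drift back (38.5/37.2/35.2% at m = 8).

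**The case against.** A reader might infer that the error always flatters the software. The documents do not support that. Section 1 makes the post-intervention phase a control too, and the RNOH target of about 40 cases without the software fits both control phases together (2 + 2 fortnightly meetings x at most 10 = 40). The colorectal target of 120 fits one 4-week phase (4 x 30), so the intended control is not settled. Against the pooled control, step 6 shows dropped-case medians making the software look slower. This objection stands on direction; a distortion remains either way.

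A reader might also infer that the protocol drops open cases. It does not say so. Section 8.5 includes all discussed cases for the complex-case MDTs, and ranking open cases as longest leaves the pre vs intervention median essentially unbiased. The close and the handling of open cases are assumptions here, and an SAP could set a rule for either. What survives is that the summaries named in Sections 8.5 and 12 do not suit times unknown for some cases: the mean fails outright, and the upper quartile fails at means of 8 weeks or more.

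Scope is narrow as well. The endpoint is optional and secondary, breast is on hold, the cancer event is a decision rather than a treatment and may come quickly, and the analysis is descriptive in a pilot not powered for secondary outcomes. All of that stands and limits the importance.

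**Conclusion.** The concern holds in a limited form. Unequal follow-up by phase follows from the protocol's own calendar under any single close, and a plain mean or median by phase does not allow for it.

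Under the assumed Day 154 close, exponential times, no referral wait and open cases dropped, intervention looks faster than pre-intervention with no true effect: medians by 7% and 21%, means by 14% and 27%, at mean times of 4 and 8 weeks. The shift is negligible at 2 weeks. Post-intervention looks faster still, which would mask a return to baseline after the software is withdrawn. With a pooled control the direction varies (medians +2 to +10%, means +6 to -14%).

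The harm is a misleading descriptive summary rather than a false test. It matters mainly for slow events, which may include date of operation at RNOH.

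**What to change.** In Sections 8.5 and 12, for endpoint 9 if collected:

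- Report by phase the proportion of all discussed cases implemented within the same fixed window from discussion. A 28-day window is observable for every case under the 4-week allowance (154 - 126 = 28 days; breast 98 - 70 = 28).
- State the data close for this endpoint.
- If a time summary is also wanted, use a time-to-event estimate by phase, with open cases censored at the close and cases known never to be implemented treated as a competing event. This is optional given the small numbers at RNOH.

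The cost is a few lines of wording and one dated status per case at the close (implemented, open, or known never to be implemented). The window is short, and starting it at discussion leaves out the referral wait, which endpoint 8 covers. Intervals at RNOH will be wide: two fortnightly meetings of at most 10 cases give about 20 per control phase, and 8/20 (40%) has a Wilson 95% CI of 22-61%.

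As a separate clerical item that does not bear on the bias, reconcile Section 23 with Sections 1, 13 and 14. Section 23 gives 10 weeks after the last participant joins, with 2 weeks of data collection; the others give 18 or 10 weeks plus 4. Counted from Day 0, which is an assumption, Section 23 implies Day 70, or Day 84 if the 2 weeks are added. For the complex-case MDTs both fall inside the intervention period (Day 43-98).
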